5 TRIAL SYNOPSIS

Trial code	ATi-2
Title of Trial	A Protocol of a Multicenter, Randomized, Open-Label, Comparative Study of Therapeutic Efficacy, Safety and Tolerability of Imupret application in the therapeutic concept of delayed prescription of antibiotics in children, aged 6-12 with severe acute tonsillitis.
Working title	Imupret in tonsillitis
Trial Design	open-label, exploratory, comparative, multicentre, randomized, prospective, parallel-group study.
Clinical phase	IV
Inclusion diagnosis	Acute tonsillitis
Trial objectives	
Assessment of the influence of Imupret (drops) prescriptions in the therapeutic concept of delayed prescription of antibiotics to:
 
 • need for antibiotics • regression of the tonsillitis symptoms • duration of antipyretics administration
Number of patients	approximately N=200 (1:1 ratio active treatment: reference)
Specialization of investigator	Head of Department of Otorhinolaryngology Head & Neck Surgery
Time schedule	Planned FPI (First patient in): approximately February 2019 Planned LPO (Last patient out): approximately December 2019
Efficacy endpoints	
The main criterion (main variable):
 
 - decrease in the severity of each symptom (complaint) that is part of the Mclsaac scale of tonsillitis manifestations, up to 1 point or less. This variable is dichotomous, with the categories "treatment effective" and "treatment not effective": - Treatment is effective - reducing the severity of each symptom (complaint) that is part of the Local Tonsillitis Manifestation Scale (0-15), of tonsillitis manifestations, up to 1 point or less in the evaluation stages. Absence of indications for prescribing antibacterial therapy - Treatment is not effective - the condition given for the category "therapy is effective" is not met.
Secondary end-points	
Secondary variables:
 
 - a decrease in the severity of the symptoms of the underlying disease, at the 2- nd, 3 -rd and 4- th visits compared to the 1- st visit. - decrease in the total score (the sum of scores for each symptom) according to the scale of local manifestations of tonsillitis at the 2-nd, 3-rd and 4-th visits in comparison with the 1-st visit. - a decrease in temperature in the armpit at the 2-nd and 3-rd visits compared to the 1-st visit. - a patient's self-assessment of the quality of life (every day). - Duration of NSAID administration. -Therapy compliance

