Boundary probability error of the first kind α	0,025
The probability of an error of the second kind β	0,2
The percentage point S.N.R. for α	1,96
The percentage point S.N.R. for β	0,84
The observed frequency of the positive effect for the control group $p_{control}$	0,75
Estimated value of the positive effect for the main group p_{main}	0,90
The value of the clinically important differences d	0,15
Estimated differences between groups e	0,0
The size of the main group n_{main}	97
The size of the control group $n_{control}$	97
Estimated share of departures	3
Adjusted main group size	100
Adjusted control group size	100

The final number of patients in each group was adjusted for their possible dropout. Thus, the final number of subjects in each group was 100 patients (200 patients in total).

Test treatment	
 - Treatment with Imupret® oral drops according to the respective Summary of Product characteristics (Imupret® coated tablets or oral drops during acute period for 5 days, afterwards switch to the subacute dosage regimen for further 28 days) - Sparing diet; fractional feeding (5-6 times a day) in small portions with the exception of coarse, spicy, heavily digestible foods - Elimination of factors irritating pharyngeal mucosa (thermal, chemical) 
 - As needed, Paracetamol (Acetaminifen) in a single dose of up to 400 mg not more than 3 times daily or paracetamol in a single dose of up to 500 mg 3-4 times daily (if necessary). - Topical agents such as Benzydamine, Lidocaine as needed (in case of severe sore throat). 	
Reference treatment	
 - Sparing diet; fractional feeding (5-6 times a day) in small portions with the exception of coarse, spicy, heavily digestible foods - Elimination of factors irritating pharyngeal mucosa (thermal, chemical) - As needed, Paracetamol (Acetaminifen) in a single dose of up to 400 mg not more than 3 times daily or paracetamol in a single dose of up to 500 mg 3-4 times daily (if necessary). - Topical agents such as Benzydamine, Lidocaine as needed (in case of severe sore throat). 	
Investigational Medicinal Product	Active (add on) treatment	Imupret® oral drops

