7 TRIAL OBJECTIVES

The aims of this clinical trial are:

To investigate the influence of Imupret prescriptions in the therapeutic concept of delayed prescription of antibiotics to:

- To compare the need for antibiotics in patients, received Imupret in addition to conventional therapy and in patients of the control group (received conventional therapy only)
- To evaluate the effect of the study drug in complex with conventional therapy versus conventional therapy only on regression of the tonsillitis symptoms
- To evaluate the effect of the study drug in complex with conventional therapy versus conventional therapy only on duration of antipyretic (paracetamol as antipyretic) administration.

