8.3.3 Reference treatment

All patients of the trial will undergo the reference treatment described below. However, only one of the two study groups (study group 1) will receive and add-on treatment with either Imupret® oral solution (see 0 and 8.3.2).

Reference treatment comprises instructions for patient's behavior as well as possible medical treatment when needed:

- Sparing diet with fractional feeding (5-6 times a day) in only small portions explicitly excluding coarse, spicy, or heavily digestible food
- At the discretion of the investigator, elimination of all factors irritating pharyngeal mucosa (e.g. thermal, chemical influence etc.)

At the discretion of the investigator, Paracetamol as single doses up to 500 mg – not more than 3-4 times daily

- At the discretion of the investigator, topical treatment like benzydamine, lidocaine (in case of severe sore throat)
- At the discretion of the investigator, antibiotic treatment in case it is indicated with e.g. amoxicillin clavulanate, cephalosporins (in case of prescription of antibiotics patients will be evaluated separately)

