10.9.1 Procedure related risks

10.9.2 Risks related to the investigational medicinal product

Imupret® oral drops

The investigational products Imupret® oral drops contain the ingredients given in sections 0 and 8.3.2.

According to the Summaries of Product characteristics the following site effects and interactions may occur during intake:

Side effects

Rarely gastrointestinal disorders (e.g. abdominal pain, nausea, vomiting) may occur. Allergic reactions (e.g. rash, itching, dyspnea) may also occur.

When taken together with preparations containing matricaria flowers and also in patients with hypersensitivity to other plants of the Composite family (e.g. Yarrow herb (*Achillea Millefolium*)) allergic reactions may occur. In case of any undesirable side effects the use of the medicinal product should be discontinued and a doctor should be consulted.

Interactions with other medicines and other forms of interaction

No interactions with other medicines have been reported. When using preparations which contain oak bark, the resorption of alkaloids and other alkaline medicinal agents may be reduced or blocked if taken together.

Overdose

No cases of intoxication due to overdose has been reported.

Reference treatment

At the discretion of the investigator, Paracetamol as single doses up to 500 mg – not more than 3-4 times daily will be prescribed. Moreover, at the discretion of the investigator, topical treatment with e.g. benzydamine, lidocaine (in case of severe sore throat) may be prescribed. In

case an antibiotic treatment will be necessary, the investigator may prescribe e.g. amoxicillin clavulanate, cephytryaxons etc.

As it is not yet known, what kind of prescription will be exactly done by the investigator, possible side effects and interactions are hardly to be described in here in the protocol. In any case the investigator has to inform the patient and (or) his/her parent(s) about the risks related to the intake of Reference medication according to the respective Summaries of Product Characteristics.

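### The synopsis gives two limits for as-needed paracetamol with no rule for choosing between them; sections 8.3.3 and 10.9.2 carry only one of the two

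*Protocol*

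**What the plan says.** The synopsis lists paracetamol, as needed, in both the Test treatment and the Reference treatment rows, in identical words. The first limit is "in a single dose of up to 400 mg not more than 3 times daily". The sentence then continues "or paracetamol in a single dose of up to 500 mg 3-4 times daily (if necessary". Paracetamol is named in both halves, and nothing says when either half applies.

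Section 8.3.3, which describes the reference treatment given to all patients, has one limit, at the investigator's discretion: "Paracetamol as single doses up to 500 mg – not more than 3-4 times daily". Section 10.9.2 repeats it in the part on risks: "Paracetamol as single doses up to 500 mg – not more than 3-4 times daily will be prescribed". Neither section contains the 400 mg limit.

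Antipyretic use also appears among the objectives. The synopsis lists "duration of antipyretics administration", and section 7 is more specific: "duration of antipyretic (paracetamol as antipyretic) administration". Elsewhere the terms change. Section 8.1 describes standard therapy as including NSAID, and the synopsis has the duration of NSAID administration as a secondary endpoint, although paracetamol is the only antipyretic that the treatment sections name.

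**The concern.** This is an operative treatment instruction for children aged 6 to 12. A site working from the synopsis finds two maxima for one drug; a site working from section 8.3.3 or 10.9.2 finds one. The documents do not say whether the synopsis or the body of the protocol takes precedence, or what would make a child subject to the lower entry rather than the higher.

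The main stake is patient safety: a rule on the maximum amount of a medicine for children should be readable in only one way. A lesser stake is consistency of background treatment. Paracetamol can act on fever and pain, and axillary temperature and throat-pain scores are among the outcomes, so sites that read the limit differently would be giving somewhat different background care.

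**Working it through.** The documents state no daily total for paracetamol, so there is no figure of the plan's own to reproduce. The check uses maximum single dose × maximum number of doses per day.

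**Inputs**
- Synopsis, first entry (both arms): 400 mg, 3 times daily.
- Synopsis, second entry (both arms): 500 mg, 3 to 4 times daily.
- Section 8.3.3: 500 mg, 3 to 4 times daily.
- Section 10.9.2: 500 mg, 3 to 4 times daily.

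**Daily maximum**
- First entry: 400 × 3 = 1200 mg.
- Second entry, and sections 8.3.3 and 10.9.2: 500 × 3 = 1500 mg, up to 500 × 4 = 2000 mg.

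**Ratio of second entry to first**
- At 3 doses: 1500 / 1200 = 1.25, the same as the single-dose ratio 500 / 400 = 1.25.
- At 4 doses: 2000 / 1200 = 1.67.

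**Where the 1.67 comes from**
- Double entry (single dose): 1.25.
- Frequency stated as a range: 4 / 3 = 1.33.
- Product: 1.25 × 1.33 = 1.67.

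The 1.33 is an imprecision in every statement of the 500 mg limit and would remain if the 400 mg entry were absent. The double entry itself adds the 1.25 in dose, together with a firm limit of three doses that the other entry does not share.

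**Does the word *or* settle it?** Suppose both entries are permitted options. Any use within 400 mg three times daily then also lies within 500 mg three to four times daily, so the first limit restricts nothing. A maximum with no effect is either redundant or meant for a subgroup or situation that the text does not describe. Neither reading tells a site what to do.

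**Who is affected?** The wording covers all of the approximately 200 planned children. Dosing is as needed and discretionary, and the documents do not say how many will take paracetamol or come near either limit.

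**The case against.** The strongest reply is that nothing here is a strict contradiction. The entries are joined by *or*, the outer limit of 500 mg is the same in all three places, and no section forbids what another allows. On this view the synopsis merely carries an unexplained lower option. That is right as far as it goes, and it is why the point is an ambiguity rather than two rules that cannot both be followed. It does not remove the problem, because the lower limit is worded as a maximum and then has no effect, with no criterion for its use.

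Several stronger readings are tempting, and the documents do not support them.

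- **That the wording biases the comparison.** The sentence is the same in both arms. Uneven use between arms could arise from open-label, discretionary dosing, but that would remain with a single limit and is a separate matter.
- **That it directly distorts a trial objective.** The objective concerns how long antipyretics are given, not the daily amount. A different daily maximum might alter how long the drug is needed, but the documents give no basis for estimating this.
- **That one entry was meant for a different drug.** The repeated drug name and the stray NSAID label invite this. Section 7 names paracetamol as the antipyretic, and sections 8.3.3 and 10.9.2 name no other, so it remains conjecture.
- **That one of the limits is unsafe.** The documents contain no standard against which to judge either.
- **That paracetamol use goes unrecorded.** Medication checks are planned at Visits 2, 4 and 5, and the case report form is not among the documents, so this cannot be judged.

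**Conclusion.** The point holds as an internal inconsistency in a treatment instruction for children. The synopsis gives two limits for as-needed paracetamol in both arms without a rule for choosing, and sections 8.3.3 and 10.9.2 give only one of them. The implied daily maxima differ by a factor of 1.25 to 1.67, the upper figure being the extreme case that also absorbs the 3-to-4 frequency range.

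This assumes that the 500 mg entry in the synopsis, which states a frequency without the words of a cap, is meant as a maximum, as it is worded in sections 8.3.3 and 10.9.2. It also assumes that no other trial document, such as a site manual, settles the matter.

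The finding shows no bias towards either arm, and it supports no estimate of an effect on any endpoint. It should be corrected because the rule concerns the safety of children and the correction is simple.

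**What to change.** The sponsor's clinicians should reconcile the Test treatment and Reference treatment rows of the synopsis with sections 8.3.3 and 10.9.2, so that one antipyretic rule appears in all of them. If two limits are intended, the text should say in every place what decides between them. The frequency should also be stated as a single maximum or its range explained. Which limit applies is for the clinicians, and no view is taken here.

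The terms should be aligned at the same time. The NSAID wording in section 8.1 and in the synopsis secondary endpoint should agree with section 7, which speaks of paracetamol as the antipyretic, so that the objective and the endpoint refer to the same medicine.

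The cost is an edit to a few lines of the protocol and notice of the change to sites. Sample size, visit schedule and analysis are unaffected.

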	Mode of administration and dosage regimen	
Imupret® oral drops
 
Dosage for acute symptoms:
 
Children from 6 to 12 years: 15 drops 5-6 times daily
 
Adults and adolescents from the age of 12 years: 25 drops 5-6 times daily
 
Dosage after acute symptoms have subsided:
 
Children from 6 to 12 years: 15 drops 3 times daily
 
Adults and adolescents from the age of 12 years: 25 drops 3 times daily

Duration of treatment	
Disease will be evaluated 36-48 hours prior to active treatment.
 
Active Imupret® treatment group: 10 treatment days
 
Reference treatment group: 10 days
 
Afterwards, there will be a follow up observation phase of 1 months
	

SCHEDULE OF ASSESSMENTS

V1		V2		V3 (Telephone call)					V4	V5
day 1	day 2	day 3	day 4	day 5	day 6	day 7	day 8	day 9	day 10	day 28

Study group 1

Imupret (dosage acute phase)
Reference treatment

Study group 2

Reference treatment

V1	day 1	Screening, randomization, prescription of treatment
V2	day 3	Status evaluation, possible prescription of antibiotics
V3	day 5 ±1	Evaluation of treatment efficacy, telephone call
V4	day 10 ±1	Evaluation of treatment efficacy, end of reference treatment
V5	day 28	Telephone call

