8 TRIAL PLAN

8.1 Trial design

This is an open-label, exploratory, comparative, multicenter, randomized, prospective, parallel-group phase IV clinical trial. The trial is designed in order to reveal effects of an additional Imupret therapy in comparison to the standard therapy alone (diet, NSAID, elimination of irritative factors, local anaesthetics).

Imupret® oral solution is registered and marketed in the Ukraine. The dose of Imupret was selected based on the recommendations given in the respective Summary of Product Characteristics of both dosage forms, which is also reflected in the package leaflet, respectively.

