8.3.2 Imupret® oral solution

The composition of the medicinal product is as follows:

Active substances: 100 g drops contain 29 g of an alcoholic aqueous extract (extracting agent: ethanol 59% (V/V) made from the following medicinal plants:

Marshmallow root (Radix Althaeae)	0,4 g;
Camomile flowers (Flores Chamomillae)	0,3 g;
Horstail herb (Herba Equiseti)	0,5 g;
Walnut leaves (Folia Jungladis)	0,4 g;
Yarrow herb (Herba Millefolii)	0,4 g;
Oak bark (Cortex Quercus)	0,2 g;
Dandelion herb (Herba Taraxaci)	0,4 g;

Excipients: Ethanol 19 % (V/V), purified water.

Pharmaceutical form: Oral drops.

Clear or slightly turbid yellow-brown fluid with characteristic taste and chamomile aroma. Turbidity or flocculation may occur during storage.

Name and address of the manufacturer.

Bionorica SE, [name].

Indications. Diseases of the upper respiratory passages (tonsillitis, pharyngitis, laryngitis). Prevention of complications and recurrences in patients with respiratory viral infections caused by the reduced resistance of the organism.

Age	Dosage for acute symptoms	Dosage after acute symptoms have subsided and for prophylactic treatment
Children of 1 year of age	5 drops 5 – 6 times daily	5 drops 3 times daily
Children from 2 to 5 years	10 drops 5 – 6 times daily	10 drops 3 times daily
Children from 6 to 11 years	15 drops 5 – 6 times daily	15 drops 3 times daily
Adults and adolescents from the age of 12 years	25 drops 5 – 6 times daily	25 drops 3 times daily

However, only patients from the age of 6 upwards will be included in the trial.

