9.2 Inclusion criteria

- Children (males/females), 6 - 12 years old, with severe acute tonsillitis.
- Possibility to initiate therapy within 72 hours since the onset of the disease symptoms.
- Score 4-5 according to Mclsaac Scale.
- Patient's and (or) one of his/her parents' willingness and ability to fulfil the requirements of the Study Protocol.
- Signed informed consent of the patient and (or) his/her parents for participation in the study.

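### A 12-year-old in the Imupret arm fits two dose rows in the synopsis, while section 8.3.2 ends the lower-dose row at age 11; the two tables need to be reconciled.

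*Protocol*

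**What the plan says.** **Eligibility.** Protocol section 9.2 admits "Children (males/females), 6 - 12 years old, with severe acute tonsillitis". The synopsis repeats this criterion, and the trial title gives the same age range. No text says whether the upper limit includes the year between the 12th and 13th birthdays.

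**Synopsis, mode of administration and dosage regimen.** The acute-phase rows are "Children from 6 to 12 years: 15 drops 5-6 times daily" and "Adults and adolescents from the age of 12 years: 25 drops 5-6 times daily". The post-acute rows are "Children from 6 to 12 years: 15 drops 3 times daily" and "Adults and adolescents from the age of 12 years: 25 drops 3 times daily".

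**Section 8.3.2, dosage table.** The 15-drop row is headed "Children from 6 to 11 years" and the 25-drop row "Adults and adolescents from the age of 12 years". Drops per intake and intakes per day match the synopsis in both phases. Only the upper age limit of the child row differs.

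**Basis of the dose.** Section 8.1 says: "The dose of Imupret was selected based on the recommendations given in the respective Summary of Product Characteristics of both dosage forms". The synopsis entry for the test treatment also refers to the product information, and section 8.3.3 points to 8.3.2 for the add-on treatment. No passage says which table governs if the two differ.

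**The concern.** On the plain wording of the synopsis, age 12 belongs to both rows, and section 8.3.2 places it in only one. Two sites could each follow the protocol to the letter and give 12-year-olds different daily doses.

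What is at stake for the analysis is limited but concrete. The synopsis lists therapy compliance as a secondary variable, section 9.4.1 allows withdrawal for poor compliance, and the per-protocol set (protocol 12.2.1 and the SAP's analysis sets) excludes patients with major protocol deviations. Each of these needs one intended dose per child. For a 12-year-old, the same intake could count as adherent under one row and as an under- or overdose under the other. The SAP has no rule that would settle this afterwards.

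**Working it through.** **1. Daily drops by row.** Drops per day = drops per intake × intakes per day. The inputs are the four synopsis rows; the drop counts and frequencies in 8.3.2 are the same.

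| Phase | Intakes/day | 15-drop row | 25-drop row |
|---|---|---|---|
| Acute | 5 | 15 × 5 = 75 | 25 × 5 = 125 |
| Acute | 6 | 15 × 6 = 90 | 25 × 6 = 150 |
| Post-acute | 3 | 15 × 3 = 45 | 25 × 3 = 75 |

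**2. Size of the gap.**
- At equal frequency the intakes cancel: 25/15 − 1 = 66.7%. Put the other way, the lower dose is 1 − 15/25 = 40% below the higher.
- Both rows allow 5 or 6 intakes in the acute phase, so the gap there runs from 125/90 − 1 = 39% to 150/75 − 1 = 100%.
- In the post-acute phase frequency is fixed at 3, so the gap is 67%.

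**3. Which readings of 6 to 12 produce the conflict.**

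| Inclusion range | Synopsis child row | Result |
|---|---|---|
| Includes age 12 | Includes age 12 | Two doses in the synopsis; child row conflicts with 8.3.2 |
| Includes age 12 | Stops at 12th birthday | One dose, agreeing with 8.3.2, but the same range is read two ways |
| Stops at 12th birthday | Either | No 12-year-old is eligible; nobody is affected |

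The protocol does not choose among these. Its other age bands suggest inclusive upper limits: in 8.3.2 a band ending at 5 is followed by one starting at 6, and a band ending at 11 by one starting at 12; in the McIsaac table (section 10.6) a band ending at 14 is followed by one starting at 15. Under that convention, 6 to 12 takes in the whole of age 12, and the first line of the table applies.

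**4. How many children.** The documents give no age distribution. With 100 patients planned for the Imupret arm and even recruitment over the seven age-years 6 to 12 (assumption), 100/7 = 14.3, or about 14. If 12-year-olds are not eligible, the number is 0. Fourteen is not a strict ceiling, but section 6.1 remarks that the disease is frequent in early school age, which points below it.

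**The case against.** The best defence is that the two synopsis rows adjoin and meet at the 12th birthday. Read that way, they agree exactly with 8.3.2, and if the inclusion range is read the same way no 12-year-old enters the trial. This reading is possible, and it is why the overlap cannot be called certain. It does not remove the need for clarification, because the protocol never states it. Keeping 12-year-olds eligible while avoiding the overlap means reading one range in two ways.

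A second defence is that 8.3.2 on its own is unambiguous, and that the dose is tied to the product information. Both statements are correct, so a site is not without guidance. But nothing gives 8.3.2 precedence over the synopsis, and the protocol reproduces the dosing bands with two different age limits. The product information is not among the documents, so whether it settles age 12 cannot be checked here.

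Two stronger conclusions are tempting and are not supported:

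- **That the discrepancy endangers children.** Both figures are listed doses for neighbouring age bands. Section 6.2.1.2 describes few reactions, and section 10.9.2 says no intoxication from overdose has been reported. The documents show no harm from either row.
- **That the Imupret arm as a whole is not a defined treatment.** Both tables give ages 6-11 the same dose, and dosing is banded by age by design. No effect on an endpoint or on the between-arm comparison is shown.

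**Conclusion.** The inconsistency is real and should be corrected, with a narrow scope. It concerns only 12-year-olds in the Imupret arm, and it arises from the synopsis wording and its mismatch with 8.3.2, not from 8.3.2 itself.

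If age 12 is eligible and the synopsis is taken as written, these children have two documented doses with the daily gaps shown above. The 67% figure assumes equal intake frequency; the 39% to 100% range covers the permitted 5-6 acute-phase intakes. The count of 0 to about 14 of 100 depends on whether age 12 is eligible and, at its upper end, on even recruitment. The contradiction itself does not depend on that count. The analytic consequence is confined to judging compliance and dose-related deviations in these children.

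**What to change.** Reconcile the synopsis dosage rows with the 8.3.2 table so that each eligible age appears in exactly one row, with identical wording in both places and for both phases. State in section 9.2 and in the synopsis whether the age range includes children who have turned 12. Which row applies to them is for the sponsor's clinicians to decide against the product information.

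The cost is a short text correction to the protocol. Sample size and planned analyses do not change. If any 12-year-olds have already been treated, their prescribed dose should be listed, so that compliance and per-protocol status can be assessed against what they were told to take.
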